10.4.2	Evaluations.....	35
10.4.3	SAE/Unanticipated Adverse Device Effect (UADE)/Unanticipated Serious Adverse Device Effect (USADE) Reporting	35
10.4.4	Device Deficiency (DD) Reporting	36
10.5	PREGNANCY	36
10.6	POTENTIAL ADVERSE EVENTS	36
10.7	POTENTIAL BENEFITS.....	37
11	STUDY MONITORING	38
12	ETHICAL AND REGULATORY CONSIDERATIONS	39
12.1	SUBJECT INFORMATION AND CONSENT	39
12.2	DECLARATION OF HELSINKI	39
12.3	ISO 14155:2011 CLINICAL INVESTIGATION OF MEDICAL DEVICES FOR HUMAN SUBJECTS- GOOD CLINICAL PRACTICE	39
12.4	ADDITIONAL REGULATORY CONSIDERATIONS	39
12.5	STUDY INITIATION/CONDUCT.....	39
12.6	COMPLIANCE WITH THE CLINICAL STUDY PROTOCOL	39
12.7	PROTOCOL DEVIATIONS (PDs)	40
12.8	PROTOCOL AMENDMENTS.....	40
12.9	PUBLICATION POLICY	40
12.10	INSURANCE AND INDEMNITY	40
13	REFERENCES.....	41

RXSIGHT, INC.**PROTOCOL NO. CSP-032****A SINGLE CENTER EXPLORATORY STUDY TO EVALUATE THE USE OF THE
RXSIGHT LIGHT ADJUSTABLE LENS (LAL) AND THE LIGHT DELIVERY
DEVICE (LDD) TO IMPROVE VISUAL OUTCOMES****1 STUDY SYNOPSIS****STUDY OBJECTIVE**

The objective of this study is to evaluate, for the visual correction of aphakia, whether the RxSight Light Adjustable Lens (LAL) and Light Delivery Device (LDD) can be used to improve visual outcomes after performing adjustments of the LAL with the LDD. This is an exploratory study. No primary effectiveness endpoints will be identified.

STUDY POPULATION

The study population will consist of up to 200 eyes in up to 200 subjects (one or two eyes per subject).

STUDY DESIGN

A prospective, controlled, single center, exploratory clinical study will be conducted. Subjects will be followed until the completion of a Postop Month 3 or later visit. Subjects who were enrolled under protocol version 05 will be reconsented prior to undergoing a Postop Month 3 or later visit. Subjects who were enrolled under protocol version 05 and exited from the study after their Postop Months 1-2 visit will be reconsented prior to undergoing the Postop Month 3 or later visit.

Patients who require cataract extraction and intraocular lens implantation will be screened for eligibility. If one or both eyes meet inclusion/exclusion criteria, study staff will explain the study purpose, procedures, risks/benefits and subject responsibilities to the potential participant. Written informed consent will be obtained prior to any study specific testing. The patient is enrolled upon signing the informed consent. If both eyes of the subject are enrolled for study participation, each eye will be scheduled for surgery within a timeframe of the investigator's choice but on separate days.

Commencing at the Postop Week 3 visit, all eyes will receive two to three adjustments and one to two lock-in treatments. Each light treatment will be separated by 3 to 7 days. [REDACTED]

[REDACTED] Postoperatively, all subjects will undergo complete ophthalmic examinations at regular intervals.

For subjects that receive only spherical/sphero-cylindrical adjustments, distance visual acuities will be presented and summarized. For subjects that receive a presbyopia adjustment, distance, intermediate, and near visual acuities and depth of focus (DOF) curves will be

presented and summarized. Additional analyses may be performed. Safety for all study eyes will be evaluated per ISO 11979-7.

DURATION OF STUDY

Each subject will participate in the study for 3-9 months. Time of participation is dependent on the date of the Postop Month 3 or later visit. The recruitment phase is expected to last approximately 12 months. The complete study period is expected to be 14 months.

STUDY SITE

The study will be performed in an ophthalmology clinic. The investigator will be an ophthalmic surgeon, specializing in cataract surgery with implantation of intraocular lenses. Study responsibilities will be registered in a delegation log that will be kept at the investigational site. The overall responsibility at the study clinic remains with the investigator.

Both eyes of all subjects should be screened for eligibility. If at any time during the screening, an eye does not meet inclusion or exclusion criteria, screening for that eye will be discontinued.

REQUIRED INCLUSION CRITERIA

- Must sign a written Informed Consent form and be willing to undergo cataract surgery for unilateral or bilateral implantation of the LAL.
- Between the ages of 40 and 80 inclusive on the day the cataract surgery is performed.
- Study eye must have preoperative keratometric cylinder ≤ 3.50 D.
- Study eye must have a cataract causing reduction in best corrected distance visual acuity (BCDVA) to a level of 20/32 or worse with or without a glare source.
- Study eye must have BCDVA projected (by clinical estimate based upon past ocular history or retinal exam) to be 20/20 or better after cataract removal and IOL implantation.
- If only one eye of a subject is enrolled, the non-study eye must have the potential for BCDVA of 20/40 or better.
- Study eye has clear intraocular media other than cataract.
- Willing and able to comply with the requirements for study specific procedures and visits.
- Study eye has a dilated pupil diameter of ≥ 7.0 mm.
- Study eye has an undilated distance viewing pupil diameter >2.5 mm.
- Study eye requires an IOL power within the range available for the LAL.

OPTIONAL INCLUSION CRITERIA

- Study eye was previously enrolled within clinical study CSP-026 sponsored by RxSight, Inc.

REQUIRED EXCLUSION CRITERIA

- Serious co-morbid conditions that in the judgment of the investigator makes inclusion in the study not in the best interest of the subject.
- Study eye with pseudoexfoliation.
- Study eye with diabetes with any evidence of retinopathy.
- Study eye with evidence of glaucomatous optic neuropathy.
- Study eye with history of uveitis.
- Study eye with significant anterior segment pathology, such as rubeosis iridis, aniridia, or iris coloboma.
- Study eye with corneal pathology or corneal dystrophy that is either progressive or sufficient to reduce BCDVA to worse than 20/20.
- Study eye with clinically significant dry eye syndrome (DES).
- Study eye with keratoconus or suspected of having keratoconus.
- Study eye with prior history of Intacs, Radial keratotomy (RK), Conductive keratoplasty (CK), Astigmatic keratotomy (AK), Phakic Implantable Collamer Lens (ICL), Corneal Inlay, intraocular surgery, or with previous pterygium excision unless the pterygium did not extend more than 2mm onto the cornea from the limbus.
- Subjects taking systemic medication that may increase sensitivity to UV light such as tetracycline, doxycycline, psoralens, amiodarone, phenothiazines, chloroquine, hydrochlorothiazide, hypericin, ketoprofen, piroxicam, lomefloxacin, and methoxsalen. LDD treatment in patients taking such medications may lead to irreversible phototoxic damage to the eye. This is only a partial list of photosensitizing medications. Please evaluate all medications that the patient is taking for this effect prior to consideration for implantation.
- Subjects taking a systemic medication that is considered toxic to the retina such as tamoxifen.
- Study eye with irregular astigmatism.
- Study eye with a history of ocular herpes simplex virus.
- Subjects who the doctor believes will be unable to maintain steady fixation that is necessary for centration of the LDD light treatment.
- Study eye with previous trauma or developmental defects in which appropriate support of the intraocular lens (IOL) is not possible.
- Study eye with current vitreoretinal disease or are at a high risk for future vitreoretinal disease that may require silicone oil as part of therapy.

OUTCOME PARAMETERS

The following visual performance parameters will be collected and summarized for subjects that received only spherical/sphero-cylindrical adjustments.

- % of eyes with UCDVA of 20/20 or better at Postop Month 1-2 and the Postop Month 3 or later visit

The following visual performance parameters will be collected and summarized for subjects that were bilaterally implanted with the LAL and received a presbyopia adjustment.

- Proportion of subjects simultaneously with (1) Binocular UCDVA of 20/20 or better and (2) Binocular UCIVA of 20/25 or better and (3) Binocular UCNVA of 20/40 or better at Postop Month 1-2 and the Postop Month 3 or later visit
- Change in pseudoaccommodation (D) at Postop Month 1-2 and the Postop Month 3 or later visit from pre-light adjustment at Postop Week 3

Additional analyses may be performed. Clinical data for subjects receiving only spherical/sphero-cylindrical adjustments and subjects receiving a presbyopia adjustment will be summarized and analyzed separately.

Safety Parameters:

- Incidence of cumulative ocular serious adverse events defined per ISO 11979-7.

The incidence of all other adverse events will also be presented.

Subjects who agree to participate in the study will return for the listed follow-up examinations for each study eye:

Examination Schedule:

Evaluation	
Preoperative	Day -60 to Day -1
Operative	Day 0, day of surgery
Postop Day 1	Days 1 to 2 postop
Postop Week 3	Days 17 to 24 postop: Adjustment #1
Adjustment #2, if needed	3 to 7 days post Adjustment #1
Adjustment #3, if needed	3 to 7 days post Adjustment #2
Lock-in #1	3 to 7 days post final adjustment
Lock-in #2, if needed	3 to 7 days post lock-in #1
Postop Month 1-2	7 to 14 days post final lock-In
Postop Month 3 or later	≥90 days postop

Unscheduled visits falling outside the designated ranges for scheduled visits will be considered “interim” visits for data recording purposes and a report form will be completed.

Clinical Parameters:

[REDACTED]

2. Demographics
3. Ocular history including medications
4. Subjective symptoms/complaints (subject reported)
5. Compliance with UV spectacles
6. Ocular Biometry: ACD and axial length (Optical biometry)
7. Corneal Topography
8. Autorefraction
9. Corneal Keratometry
10. Vision Quality Measurement
11. Undilated Distance Viewing Pupil Diameter
12. Binocular UCDVA
13. Monocular uncorrected distance visual acuity (UCDVA)
14. Manifest Refraction
15. Monocular best corrected distance visual acuity (BCDVA)
16. Ocular Dominance Test
17. Pseudo accommodation testing
18. Mesopic binocular distance corrected contrast sensitivity testing
19. Mesopic monocular distance corrected contrast sensitivity testing
20. Photopic binocular distance corrected contrast sensitivity testing
21. Photopic monocular distance corrected contrast sensitivity testing
22. Monocular distance corrected 10% low contrast intermediate visual acuity (photopic only)
23. Monocular distance corrected intermediate visual acuity (DCIVA)
24. Monocular distance corrected intermediate visual acuity (DCIVA) with +1.50 D add
25. Monocular uncorrected intermediate visual acuity (UCIVA)
26. Binocular UCIVA
27. Undilated Intermediate Viewing Pupil Diameter
28. Monocular distance corrected 10% low contrast near visual acuity (photopic only)
29. Monocular distance corrected near visual acuity (DCNVA)
30. Monocular distance corrected near visual acuity (DCNVA) with a +2.50 D add
31. Monocular uncorrected near visual acuity (UCNVA)
32. Binocular UCNVA
33. Undilated Near Viewing Pupil Diameter

- 35. Intraocular pressure
- 36. Slit Lamp Examination
- 37. Fundus Exam
- 38. Aberrometry
- 39. Dilated pupil diameter
- 40. Adverse Events

ABBREVIATIONS AND DEFINITION OF TERMS

ACD	Anterior Chamber Depth
ADE	Adverse Device Effect
AE	Adverse Event
BCDVA	Best Corrected Distance Visual Acuity
CCC	Continuous Circular Capsulorhexis
CDRH	Center for Devices and Radiological Health
CFR	Code of Federal Regulations
CRF	Case Report Form
CRO	Contract Research Organization
CSP	Clinical Study Protocol
D	Dioptr
DCIVA	Distance Corrected Intermediate Visual Acuity
DCNVA	Distance Corrected Near Visual Acuity
DD	Device Deficiency
DES	Dry Eye Syndrome
DOF	Depth of Focus
EC	Ethics Committee
EDC	Electronic Data Capture
ETDRS	Early Treatment Diabetic Retinopathy Study
FDA	Food and Drug Administration
GCP	Good Clinical Practice
IDE	Investigational Device Exemption
IOL	Intraocular Lens
IOP	Intraocular Pressure
IRB	Institutional Review Board
ISO	International Organization for Standardization
LAL	RxSight Light Adjustable Lens
LD	Light Delivery Device
MR	Manifest Refraction
MRSE	Manifest Refraction Spherical Equivalent
PCO	Posterior Capsular Opacity
PMA	Premarket Application
PMMA	Polymethylmethacrylate
PPC	Precision Pulse Capsulotomy
[REDACTED]	[REDACTED]
SAE	Serious Adverse Event
SE	Spherical Equivalent

SPK	Superficial Punctate Keratitis
SSI	Secondary Surgical Intervention
UADE	Unanticipated Adverse Device Effect
UCDVA	Uncorrected Distance Visual Acuity
UCIVA	Uncorrected Intermediate Visual Acuity
UCNVA	Uncorrected Near Visual Acuity
UP	Unanticipated Problem
UV	Ultraviolet

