7.2 SUBJECT ENTRY

Patients who require cataract extraction and intraocular lens implantation will have both eyes screened for eligibility. If one or both eyes meet inclusion/exclusion criteria, study staff will explain the study purpose, procedures, risk/benefits and subject responsibilities to the potential participant. Written informed consent will be obtained prior to any study specific testing. The patient is enrolled upon signing the informed consent. The subject will sign and date the informed consent form in the presence of the person conducting the consent process. The investigator and/or the person conducting the consent process will also sign and date the consent form. During the study, the subject will be provided with any new information that is received that could affect their health status or change their willingness to continue to participate in the study. The preoperative examination will be performed no more than 60 days prior to surgery. If the 60-day time period elapses, it is acceptable for patients to be re-screened by undergoing a complete preoperative examination. Ocular dominance testing will be performed as part of the preoperative evaluation to determine eye dominance. If both eyes of the subject are enrolled for study participation, each eye will be scheduled for surgery within a timeframe of the investigator's choice but on separate days.

Only subjects meeting all inclusion/exclusion criteria will be implanted. Those subjects who do not meet the inclusion/exclusion requirements will be considered screen failures. Unique identification numbers will be assigned to each subject.

The implant lens power for the LAL will be calculated based upon the ocular biometry data and a lens power formula of the surgeon's choice. A postoperative spherical equivalent (SE) outcome of the physician's choice will be targeted.

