7.4 EXAMINATION SCHEDULE

Subjects who agree to participate in the study will return for the listed follow-up examinations for each study eye:

Evaluation	
Preoperative	Day -60 to Day -1
Operative	Day 0, day of surgery
Postop Day 1	Days 1 to 2 postop
Postop Week 3	Days 17 to 24 postop: Adjustment #1
Adjustment #2, if needed	3 to 7 days post Adjustment #1
Adjustment #3, if needed	3 to 7 days post Adjustment #2
Lock-in #1	3 to 7 days post final adjustment
Lock-in #2, if needed	3 to 7 days post lock-in #1
Postop Month 1-2	7 to 14 days post final lock-in
Postop Month 3 or later visit	≥90 days postop

Unscheduled visits falling outside the designated ranges for scheduled visits will be considered “interim” visits for data recording purposes and a report form will be completed.

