7.7.1 SUBJECT COMPLETION

Subjects are considered to have completed the study if they have completed the Postop Month 3 or later visit.

Subjects with ocular serious adverse events or adverse device effects that are unresolved at study exit should continue to be followed until resolution of the event or until they are stable per the investigator's evaluation.

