7.7.4 SUBJECT DISCONTINUATION AFTER IMPLANTATION

After implantation, subjects may not be withdrawn from the study unless the study lens has been explanted. In the case of an explant, the investigator should continue follow-up for a period that ensures no adverse consequences have resulted. When possible, all necessary clinical assessments will be performed prior to the Subject exiting the study even if the assessment was not scheduled at that particular visit.

Subjects may be discontinued from the study only when the study lens has been explanted or subject has deceased. The reason for discontinuation will be recorded on the appropriate study worksheet. Subjects who are discontinued from the study will still be a part of the study analyses up until the point they are exited.

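### Is the expected 14-month study period too short for the final visit, and does the Month 3 or later summary need visit-day and recall tables?

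*Combined protocol and SAP*

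**What the plan says.** The synopsis gives three durations together. For the individual: "Each subject will participate in the study for 3-9 months", depending on when the last visit takes place. For the study: "The recruitment phase is expected to last approximately 12 months. The complete study period is expected to be 14 months". Section 4 repeats the 3-9 month statement. The text after it is redacted, so the 12-month and 14-month figures can be read only in the synopsis.

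Section 7.4 sets the last visit at "≥90 days postop" with no upper limit. Section 7.7.1 ties completion to that visit: "Subjects are considered to have completed the study if they have completed the Postop Month 3 or later visit". Section 7.7.4 adds: "Subjects may be discontinued from the study only when the study lens has been explanted or subject has deceased". Section 7.2 counts a patient as enrolled at consent and states: "The preoperative examination will be performed no more than 60 days prior to surgery".

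Section 4 provides for version 05 subjects, including those who left after the Month 1-2 visit, to be reconsented before the Month 3 or later visit. Section 5 reports each effectiveness outcome at those two visits. Section 8.1.1 tabulates acuity by visit as counts and percentages of eyes, split by type of adjustment.

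**The concern.** Adding the recruitment length to the shortest possible follow-up of the last subject gives more than the stated total. A reader who plans around 14 months, or who wonders whether the last subjects will be followed in full, has reason to ask which figure is right. If follow-up were cut off at 14 months, the last subjects recruited would miss one of the only two post-treatment outcome visits.

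The second worry is about what the Month 3 or later label covers. It combines visits at quite different times after surgery, and it mixes continuously followed subjects with version 05 subjects who had exited and came back. If those who agreed to return differ from those who did not, the percentage at this visit could move away from the Month 1-2 percentage with no change in any eye. The plan does not commit to showing the actual day of the visit or the number recalled.

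**Working it through.** Inputs: recruitment about 12 months, total 14 months, participation 3-9 months (synopsis, Duration of Study); last visit at day 90 or later (Section 7.4); preoperative examination up to 60 days before surgery (Section 7.2). One month = 365.25/12 = 30.44 days. Total = recruitment + follow-up of the last subject.

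**Can 14 months be reproduced?**

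- Last subject enrolled and operated on at month 12, seen on day 90: 12 + 90/30.44 = 12 + 2.96 = 14.96 months. Using the synopsis alone: 12 + 3 = 15.
- Last subject consented at month 12 and using the whole 60-day window: 12 + 150/30.44 = 16.93 months.
- Last subject using the full 9 months: 12 + 9 = 21 months.

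Taken literally, no. The smallest shortfall is 14.96 - 14 = 0.96 month, about 7% of 14.

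**What recruitment length would give 14?**

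- Surgery almost at consent, visit on day 90: 14 - 2.96 = 11.04 months.
- Full 60-day window, visit on day 90: 14 - 4.93 = 9.07 months.

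The first is a tolerable reading of an approximate 12. The second is not. Fourteen months is therefore optimistic, but not excluded.

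**What depends on the 14 months?**

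- Section 9.2 starts the final analysis when all eyes have had the last visit or been discontinued, not on a date.
- Section 7.7.1 defines completion by the visit.
- Section 7.7.6 allows termination for reasonable cause, naming safety. It sets no calendar limit.
- Sections 3 and 9.1 state that there is no primary effectiveness endpoint, hypothesis test or sample-size basis.

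Replacing 14 by 15, 17 or 21 would change no denominator, estimate or follow-up rule.

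**How wide is the Month 3 or later visit?** The schedule has no ceiling, but participation of at most 9 months implies one. Counted from surgery, that is 9 × 30.44 = 274 days, so the visit spans about day 90 to day 274, or 184 days. Counted from an earlier consent, the ceiling comes sooner.

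**Can selective return be sized?** Let a fraction m of eyes not return, and let p and q be the success proportions in returning and non-returning eyes. The all-eyes proportion is (1 - m)p + mq. As q runs from 0 to 1 this covers a band of width m, so the band only restates the assumed missing fraction. The documents do not say how many version 05 subjects exited or returned, so m is unknown.

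**The case for a change.** The strongest case for acting is that the correction is cheap and the sum is plain. Twelve plus three is fifteen on the synopsis's own figures, and every other allowance lengthens it: the wait between consent and surgery, a second eye operated on later, a late final visit. In a study that rests wholly on description, readers should also see which eyes were measured and when. The freedom in Section 5 to add analyses is permission, not a commitment to these tables.

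The arithmetic stands, as does the observation that visit day and recall status are not among the planned displays. Consequence is what is missing. The duration figures are expectations, and the plan follows subjects by visit. Nor will every implanted subject necessarily reach the last visit: despite Section 7.7.4, Section 7.7.5 recognises subjects who refuse or cannot be reached as lost to follow-up, and recalled subjects may decline to reconsent. Counts at each visit will show such losses. Visits are assigned by postoperative window, and an exit form is required for every enrolled subject, so visit day and earlier exit should be recoverable if an analyst wants to describe them. That would be sensible in the final report, but the planned summaries are correct descriptions of the eyes tested without it.

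**Conclusion.** No change to the plan is needed. The stated study period is about one month below the literal sum of its inputs (14 against 14.96), and up to seven months below if the last subject takes the full 9 months (21 - 14 = 7). It can be met only with about 11 months of recruitment, surgery almost at consent and a last visit on day 90. This is a clerical inconsistency between approximate planning figures, with no effect on any analysis or on follow-up.

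The visit-day and recall tables would be a reasonable addition to a report, but their absence is not a defect in a descriptive exploratory plan that already shows the number of eyes at each visit and bounds participation at 9 months. The size of any selective return cannot be judged from the documents.

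This conclusion assumes that the redacted text in Section 4 attaches no calendar cut-off to the study period. The visible text, including the whole of Sections 8 and 9, contains none.

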2 INTRODUCTION AND RATIONALE

Cataract surgery is the most commonly performed procedure by the ophthalmic surgeon. It is estimated that more than 26 million cataract operations with intraocular lens (IOL) implantation were to be performed worldwide in 2017.¹ The average age of cataract patients is reported to be 65 to 70 years old, with a small percentage of cataract surgeries being performed on patients as young as in their early 40's.^{2,3} While key cataract technology advancements have resulted in important reductions in residual refractive error and improved uncorrected visual acuity, significant postoperative residual refractive error remains the most frequent cataract surgery complication. RxSight's Light Adjustable Lens (LAL) addresses the problems of residual refractive error by allowing adjustment of the spherical and cylindrical power postoperatively. The Center for Devices and Radiological Health (CDRH) of the Food and Drug Administration (FDA) approved RxSight's premarket approval (PMA) application for the LAL and Light Delivery Device (LDD) system on November 22, 2017. The system is indicated for the reduction of residual astigmatism to improve uncorrected visual acuity after removal of the cataractous natural lens by phacoemulsification and implantation of the intraocular lens in the capsular bag; in adult patients:

- With pre-existing corneal astigmatism of ≥ 0.75 diopters
- Without pre-existing macular disease

The system also reduces the likelihood of clinically significant residual spherical refractive errors.

Presbyopia, which will affect approximately 2.1 billion people by 2020, is the irreversible loss of the accommodative ability of the eye that occurs due to aging.⁴ Accommodation refers to the ability of the eye to increase the refractive power of its crystalline lens in order to focus near objects on the retina.⁵ Presbyopia typically occurs in people over 40 years of age and can cause a considerable decrease in the quality of life for many of those affected.⁶ Without correction, presbyopia results in difficulty performing tasks at a customary working distance. Because most patients have daily activities that require them to read and work at near and with the increasing importance of intermediate vision to clearly see cell phones and computer monitors, patients are seeking treatment options to mitigate the effects of their presbyopia.

